Clinical Trial Protocol: 408-C-1307

Protocol Tit	le:	A Multicenter, Randomized, Dose-Ranging, Double- Masked, Placebo-Controlled Phase 2 Study Evaluating the Safety and Efficacy of RTA 408 Ophthalmic Suspension for the Treatment of Ocular Inflammation and Pain following Ocular Surgery
Protocol Nu	mber:	408-C-1307
Study Phase	:	2
Product Na	me:	RTA 408 Ophthalmic Suspension (0.5%, 1.0%)
IND Numbe	er:	
Indication:		Inflammation and Pain Associated with Ocular Surgery
Investigator	s:	Multi-center clinical investigation
		Reata Pharmaceuticals
Sponsor:		[name]
Contract Re Organizatio	esearch n:	
IRB/IEC:		
		Date
	Original Protocol:	21-Nov-2013

Confidentiality Statement

10-Feb-2014

Amendment 1:

This protocol contains confidential, proprietary information of CRO and/or Reata Pharmaceuticals. Further dissemination, distribution or copying of this protocol or its contents is strictly prohibited.

SPONSOR PERSONNEL

CRO PERSONNEL

-

SYNOPSIS

Г

Protocol Title:	A Multicenter, Randomized, Dose-Ranging, Double-Masked, Placebo-Controlled Phase 2 Study Evaluating the Safety and Efficacy of RTA 408 Ophthalmic Suspension for the Treatment of Ocular Inflammation and Pain following Ocular Surgery
Protocol Number:	408-C-1307
Study Drug:	 RTA 408 Ophthalmic Suspension 0.5% RTA 408 Ophthalmic Suspension 1.0% Placebo for RTA 408 Ophthalmic Suspension
Study Phase:	Phase 2
Primary Objective:	To evaluate the clinical efficacy and safety of two concentrations of RTA 408 Ophthalmic Suspension against placebo in the treatment of patients with inflammation and pain following ocular surgery
Secondary Objective:	None
Overall Study Design	
Structure:	Multi-center, double-masked, randomized, placebo- controlled, dose-ranging, efficacy study
Duration:	Approximately 21 to 49 days (6 study visits)
Controls:	Placebo for RTA 408 Ophthalmic Suspension

T

Г

Dosage/Dose Regimen:	 Patients will be randomized in a 1:1:1 ratio to one of the following groups for BID dosing in the study eye in the morning and evening (approximately 12 hours apart) for 14 days: RTA 408 Ophthalmic Suspension 0.5% RTA 408 Ophthalmic Suspension 1.0% Placebo for RTA 408 Ophthalmic Suspension
Summary of Visit Schedule:	 Visit 1, Day ≥ -28: Screening, Baseline Evaluation Visit 2, Day 1 (24 ± 6 hours post-surgery): Study enrollment, Randomization, and 1st Study Drug Dose Visit 3, Day 4 (± 1): On Treatment Follow-up; Inflammation and Pain Assessments Visit 4, Day 8 (± 1): On Treatment Follow-up; Inflammation and Pain Assessments Visit 5, Day 15 (+ 1): Inflammation and Pain Assessments after End of Treatment Visit 6, Day 21 (± 1): Post-Treatment Follow-up; Exit Visit
Measures Taken to Reduce Bias:	Randomization will be used to avoid bias in the assignment of patients to treatment, to increase the likelihood that known and unknown patient attributes are evenly balanced across treatment groups, and to enhance the validity of statistical comparisons across treatment groups. Masked treatment will be used to reduce potential bias during data collection and evaluation of clinical endpoints.

ſ

٦

Study Population Characteristics		
Number of Patients:	Approximately 105 patients will be enrolled in this study to complete 93 patients: 31 per arm	
Condition/Disease:	Inflammation and pain following ocular surgery	
Inclusion Criteria:	 Patients must: 1. Have provided written informed consent, approved by the appropriate institutional review board; 2. Be able to comply with study requirements and visit schedule; 3. Be greater than or equal to 18 years of age of either sex or any race; 4. Have undergone unilateral cataract extraction via phacoemulsification and posterior chamber intraocular lens (PCIOL) implantation in the study eye on the day prior to study enrollment/randomization; 5. Have a grade of ≥ 2 in anterior chamber cell score on day after surgery (Day 1) in the study eye; 6. Have a potential post-operative pin-hole visual acuity (VA) < 1.0 logarithm of the minimum angle of resolution (logMAR) in the operative eye and fellow eye as measured using an Early Treatment for Diabetic Retinopathy Study (ETDRS) chart; 7. (For females of childbearing potential) agree to have urine pregnancy testing performed at screening (must be negative) and at exit visit; must not be lactating; and must agree to use a medically acceptable form of birth control¹ throughout the study duration. Women of childbearing potential include all females who have experienced menarche and have not experienced menopause (as defined by 	

¹Acceptable forms of birth control are spermicide with barrier, oral contraceptive, injectable or implantable method of contraception, transdermal contraceptive, intrauterine device, or surgical sterilization of partner. For non-sexually active females, abstinence will be considered an acceptable form of birth control.

	amenorrhea for greater than 12 consecutive months) or have not undergone successful surgical sterilization (hysterectomy, bilateral tubal ligation, or bilateral oophorectomy).
Exclusion Criteria:	 Patients must not: Have any intraocular inflammation present in the study eye during the screening slit lamp examination; Have a score greater than "0" on the Ocular Pain Assessment at Screening in the study eye; Have an immunosuppressive disease or an autoimmune disease that in the opinion of the Investigator could affect the quality of the ocular surface; Have active or chronic/recurrent ocular or systemic disease that is uncontrolled and will likely affect wound healing; Currently have suspected or known malignancy or is currently receiving antineoplastic therapy; Be a female who is currently pregnant, planning a pregnancy, lactating, not using a medically acceptable form of birth control throughout the study duration, or has a positive urine pregnancy test at screening; Use anti-inflammatory agents, analgesics/pain relievers (including opioids, narcotics and other pain medications) or immunomodulating agents, systemically, or in the study eye, and/or use medications for benign prostatic hyperplasia (BPH), from the washout period through the duration of the study. Washout periods for medications prior to surgery are as follows: Medications for BPH (tamsulosin, silodosin, alfuzosin, finasteride): 28 days Systemic corticosteroids: 14 days Systemic analgesics/pain relievers (e.g., gabapentin, pregabalin, NSAIDs and opioids): 14 days Note: Use of acetaminophen (up to 4,000 mg/day) and 'baby' aspirin (up to 81 mg/day) during the study are allowed. Use of an opioid during cataract surgery is allowed.

d. Periocular injection of any corticosteroid
solution: 28 days
e. Corticosteroid depot in the study eye: 56
f Cyclosporine: 56 days
g. Topical ocular corticosteroid: 7 days
h. Topical ocular NSAID: 7 days
8. Have glaucoma or be taking medications to treat
glaucoma in the study eye;
9. Have an intraocular pressure (IOP) $\leq 5 \text{ mmHg}$
10 Currently have or have a history of Hernes
Simplex Keratitis in the study eve:
11. Have active corneal abrasions or ulcers in the
study eye;
12. Have active or a history of chronic or recurrent
inflammatory eye disease (e.g. iritis, scleritis,
uveitis, iridocyclitis, rubeosis iritis) in the study
eye; 13 Have evidence of acute external ocular
infections (bacterial, viral and/or fungal such as
vaccinia, varicella, and other viral diseases of the
cornea and conjunctiva); tuberculosis of the eye;
corneal dystrophies; intraocular infections,
dysthyroid ophthalmopathy, active chalazion, or
uncontrolled blepharitis in the study eye;
14. Have uncontrolled and clinically significant dry
allowed):
15. Have proliferative diabetic retinopathy (PDR),
compromised macular function; significant
macular diseases; clinically significant macular
edema (CSME); or a history of cystoid macular
edema in the study eye;
incisional) within the past 6 months or be
planning to have laser or incisional surgery
during the study period in the study eye (other
than cataract surgery);
17. Have surgery planned or scheduled for the
contralateral eye during the study;
18. Have previous ocular trauma with visible
the study eve
19. Require the use of a contact lens or a collagen
shield within 72 hours of investigational drug

	 treatment or during the study period in the study eye; be unwilling to discontinue use of contact lenses during study period in the study eye; 20. Require use of non-diagnostic topical ophthalmic solutions (other than perioperative mydriatics, anesthetics and antiseptics, prophylactic antibiotics, lid scrubs for mild blepharitis, or artificial tears for the management of dry eye) in the study eye for the duration of the study; 21. Have known allergy or sensitivity to the investigational product or its components; 22. Have ocular hemorrhage in the study eye that interferes with evaluation of post-surgery inflammation; 23. Have undergone any other ophthalmic surgical procedure (e.g., vitrectomy, relaxing incisions, iridectomy, conjunctival excisions, use of iris hooks or other iris dilators, etc.) in addition to the cataract extraction procedure and PCIOL implantation in the study eye; 24. Have previously enrolled in this clinical study, or are planning to participate in another clinical trial during the follow-up period, that could confound the treatment or outcomes of this investigation; 25. Be excluded if the Investigator determines that the patient should not be included for reasons not already specified (e.g., systemic or other ocular disease/abnormality), if the health of the patient or the validity of the study outcomes may be compromised by the patient's enrollment.
Study Formulation:	The drug product is a sterile aqueous suspension formulation
Evaluation Criteria	

Efficacy Measures:	 Hierarchical Primary Efficacy Measures a. Absence of anterior chamber cells (i.e., score of '0') at Visit 5 (Day 15) for the 1.0% concentration of RTA 408 Ophthalmic Suspension compared to Placebo b. Absence of anterior chamber cells (i.e., score of '0') at Visit 5 (Day 15) for the 0.5% concentration of RTA 408 Ophthalmic Suspension compared to Placebo a. Absence of pain (i.e., score of '0') at Visit 3 (Day 4) for the 1.0% concentration of RTA 408 Ophthalmic Suspension compared to Placebo b. Absence of pain (i.e., score of '0') at Visit 3 (Day 4) for the 1.0% concentration of RTA 408 Ophthalmic Suspension compared to Placebo b. Absence of pain (i.e., score of '0') at Visit 3 (Day 4) for the 0.5% concentration of RTA 408 Ophthalmic Suspension compared to Placebo b. Absence of pain (i.e., score of '0') at Visit 3 (Day 4) for the 0.5% concentration of RTA 408 Ophthalmic Suspension compared to Placebo b. Absence of pain (i.e., score of '0') at Visit 3 (Day 4) for the 0.5% concentration of RTA 408 Ophthalmic Suspension compared to Placebo b. Absence of pain (i.e., score of '0') at Visit 3 (Day 4) for the 0.5% concentration of RTA 408 Ophthalmic Suspension compared to Placebo b. Absence of pain (i.e., score of '0') at Visit 3 (Day 4) for the 0.5% concentration of RTA 408 Ophthalmic Suspension compared to Placebo b. Absence of anterior chamber cells at Visits 3, 4 or 6 (Days 4, 8 or 21 respectively) c. Absence of flare at Visits 3, 4, 5 or 6 (Days 4, 8, 15 or 21 respectively) d. Absence of flare at Visits 3, 4, 5 or 6 (Days 4, 8, 15 or 21 respectively)
Safety Measures:	 Slit lamp biomicroscopy Pin-hole visual acuity IOP Dilated indirect ophthalmoscopic examination AE monitoring
Other:	None
General Statistical Methods and Types of Analyses:	Efficacy Analysis: Primary efficacy analyses will first test the difference in proportion of study eyes with a grade of '0' in anterior chamber cells between the 1.0% concentration of RTA 408 Ophthalmic Suspension and placebo and between the 0.5% concentration of

RTA 408 Ophthalmic Suspension and placebo at Visit 5 (Day 15) using the Pearson chi-squared statistic.
If the proportion of patients with a grade of '0' for anterior chamber cells is statistically significantly higher for the 1.0% concentration versus placebo at a 1-sided alpha = 0.10, then the hierarchical hypothesis testing will compare the proportion of patients with absence of ocular pain at Visit 3 (Day 4) between the 1.0% concentration of RTA 408 Ophthalmic Suspension and placebo using the Pearson chi-squared statistic at a 1-sided alpha=0.10.
If the proportion of patients with a grade of '0' for anterior chamber cells is statistically significantly higher for the 0.5% concentration versus placebo at a 1-sided alpha=0.10, then the hierarchical hypothesis testing will compare the proportion of patients with absence of ocular pain at Visit 3 (Day 4) between the 0.5% concentration of RTA 408 Ophthalmic Suspension and placebo using the Pearson chi-squared statistic at a 1-sided alpha=0.10.
Additionally, 95% confidence intervals will be constructed around the difference in proportions for each primary outcome using asymptotic normal approximations. Fisher's exact tests will be employed in cases of expected counts less than five.
Sample Size:

General Considerations:
The unit of analysis in this study will be the study eye for all efficacy and safety summaries. Additionally, non-ocular adverse events will be presented at the patient level. Non-study eye safety summaries will also be presented as appropriate.
The primary analyses of all efficacy data will use last observation carried forward (LOCF) to impute missing data; data for visits after a patient is discontinued for lack of efficacy will be imputed as failures for success/failure endpoints and will be imputed using LOCF for other endpoints. To check robustness of results, sensitivity analyses of the primary efficacy data will include analyses of observed data only, imputing data from patient visits after discontinuation for lack of efficacy as failures. Other imputation methods may be applied as additional sensitivity analyses.
Per protocol analyses will use observed data only, with the exception of patients who have missing data due to discontinuation for lack of efficacy; for these patients, missing data after discontinuation will be imputed as failures for success/failure endpoints and will be imputed using LOCF for other endpoints.
Summaries for continuous variables will include the sample size (n), mean, standard deviation, median, minimum, and maximum. Summaries for discrete variables will include frequencies and percentages. Differences between treatment groups will be calculated as Test – Placebo and change from baseline will be calculated as follow-up visit – baseline. The baseline visit will be defined as the last non-missing measure prior to initiation of investigational treatment. All efficacy analyses will use a one-sided alpha=0.10 test unless otherwise stated.
The secondary efficacy variables, study eyes with absence of anterior chamber cells (Visits 3, 4 or 6), study eyes with absence of pain (Visits 4, 5 or 6) and study eyes with absence of flare (Visits 3, 4, 5 or 6) will be summarized similarly to the primary efficacy summaries. Additionally, anterior chamber cells and flare as well as pain at each visit and change from

	baseline will be summarized using continuous and discrete summary statistics.
	The sum of anterior chamber cells and flare grade will be summarized similarly to anterior chamber cells and flare separately.
	Safety Analysis:
	The primary safety analysis will summarize ocular treatment emergent AEs (TEAEs) in the study eye for all treated patients using discrete summaries at the patient and event level by system organ class and preferred term for each treatment group. A TEAE will be defined as any AE that occurs after the treatment is initiated. An additional analysis will examine ocular AEs for the non-study eye. Non- ocular TEAEs will be summarized using discrete summaries at the patient and event level by system organ class and preferred term for each treatment group. Treatment related ocular and non-ocular TEAEs will be summarized similarly. Ocular and non-ocular TEAEs will also be summarized by severity.
	The IOP data will be summarized at each visit using both continuous summaries (including change from baseline) and discrete summaries (including the proportion of patients with change in IOP from baseline ≥ 10 mm Hg and the proportion of patients with an IOP ≥ 30 mm Hg that occurs at any time following initiation of study treatment) as well as shift tables.
	Slit lamp biomicroscopy and dilated indirect ophthalmoscopic examination measures will be summarized at each visit using discrete summary statistics.
	Visual Acuity data will be summarized at each visit, using discrete summaries including change from baseline in the number of lines and the proportion of patients with worsening from previous visit of ≥ 2 lines.
Summary of Known and Potential Risks and	This study is the first clinical study to evaluate the safety and efficacy of RTA 408 Ophthalmic Suspension.

Benefits to Human Patients	The ocular tolerability of RTA 408 was evaluated in multiple nonclinical studies in rats, guinea pigs, rabbits, and monkeys. No ocular or systemic toxicity was observed and systemic exposure was very low in all species tested. Conjunctival irritation was observed in the rabbit ocular GLP toxicity study with frequent dosing (4x/day); however, this was reversible, was not observed in a non-GLP study in rabbits, was not observed in the monkey ocular GLP toxicity study, and is readily monitorable in the clinic. In vitro and in vivo studies conducted to date demonstrate that RTA 408 is a potent activator of the Nrf2 pathway and an inhibitor of the NF- κ B pathway, and should thus be an effective anti-inflammatory agent for ophthalmic indications of inflammation and pain.
----------------------------	---

TABLE OF CONTENTS

SYN	OPSIS			3	
List o	of Abb	reviatio	ns	. 17	
1	INTRODUCTION				
2	STUDY OBJECTIVES				
3	CLIN	ICAL H	YPOTHESES	. 20	
4	OVEI	RALL S	ГUDY DESIGN	. 20	
5	STUDY POPULATION				
	5.1	Number	r of Patients	. 21	
	5.2	Study P	opulation Characteristics	. 21	
	5.3	Inclusio	n Criteria	. 21	
	5.4	Exclusio	on Criteria	. 22	
	5.5	Withdra	awal Criteria	. 24	
6	STUDY PARAMETERS				
	6.1	Efficacy	V Measures	. 24	
		6.1.1	Secondary Efficacy Variables	. 24	
	6.2	Safety N	Aeasures	. 24	
	6.3	Other N	Ieasures	. 25	
7	STUD	Y MAT	ERIALS	. 25	
	7.1	Study T	reatments	. 25	
		7.1.1	Study Treatments/Formulations	. 25	
		7.1.2	Instructions for Use and Administration	. 25	
	7.2	Other S	tudy Supplies	. 25	
8	STUD	Y MET	HODS AND PROCEDURES	. 26	
	8.1	Patient	Entry Procedures	. 26	
		8.1.1	Overview	. 26	
		8.1.2	Informed Consent	. 26	
		8.1.3	Washout Intervals	. 26	
		8.1.4	Procedures for Final Study Entry		
		8.1.5	Methods for Assignment to Treatment Groups		
	8.2	Concur	rent Therapies		
		8.2.1	Prohibited Medications/Treatments		
		8.2.2	Escape Medications	. 28	
	0.0	8.2.3	Special Diet or Activities	. 29	
	8.3	Examin	ation Procedures	. 29	
		8.3.1	Procedures to be Performed at Each Study Visit with Regard	•	
	0.4	to Study		. 29	

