8.1.5 Methods for Assignment to Treatment Groups

All patients screened for the study who sign a consent form will be assigned a 3-digit screening number which will be entered in the Screening and Enrollment Log. The Patient ID number will be a 7-digit number consisting of the 4-digit site number combined with the 3-digit screening number.

Once a patient meets all qualification criteria, they will be randomly assigned to masked treatment using a 1:1:1 (0.5% RTA 408: 1.0% RTA 408: placebo) assignment ratio. Patients will be randomized on the first day post-surgery (Day 1) by assignment of the lowest 5-digit study drug kit number available at their investigative site. No study drug kit numbers will be skipped or omitted. A trained, unmasked technician will administer study drug from the bottle of the study drug kit assigned to the patient. Each study drug kit will be labeled with the 5-digit study drug kit number. The bottle of study drug will be dispensed to the patient for use on subsequent days.

8.2 **Concurrent Therapies**

The use of any concurrent medication, prescription or over-the-counter, used within the last 60 days before Visit 1 and for the duration of the study is to be recorded on the patient's source document and corresponding case report form (eCRF) along with the reason the medication was taken.

Concurrent enrollment in another investigational drug or device study is not permitted.

8.2.1 Prohibited Medications/Treatments

Prohibited medications/treatments for the duration of the study are:

- Topical ocular corticosteroid in the study eye
- Topical ocular NSAID in the study eye
- Systemic corticosteroids
- Periocular injection of any corticosteroid solution in the study eye
- Corticosteroid depot in the study eye (after implantation)
- Topical ocular cyclosporine in the study eye
- Anti-inflammatory or immunomodulating agents systemically, or in the study eye.

- Systemic medications for benign prostatic hyperplasia (BPH) (e.g., tamsulosin, silodosin, alfuzosin, finasteride).
- Systemic Analgesics/pain relievers, including opioids, narcotics and other pain medications systemically (e.g., gabapentin, pregabalin, NSAIDs and opioids).

Note: Use of acetaminophen (up to 4,000 mg/day) and 'baby' aspirin (up to 81 mg/day) during the study are allowed. Use of an opioid during cataract surgery is allowed.

- Glaucoma medications or ocular hypertension medications in the study eye
- Contact lens or a collagen shield in the study eye

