- Non-diagnostic topical ophthalmic solutions (other than perioperative mydriatics, anesthetics and antiseptics, prophylactic antibiotics, lid scrubs for mild blepharitis, or artificial tears for the management of dry eye) in the study eye
- Antineoplastic therapy
- Any other ophthalmic surgical procedure (e.g., vitrectomy, relaxing incisions, iridectomy, conjunctival excisions, use of iris hooks or other iris dilators, etc.) in addition to the cataract extraction procedure and PCIOL implantation in the study eye
- Plan to have laser or incisional surgery in the study eye (other than cataract surgery);
- Surgery planned or scheduled for the contralateral eye;

If a patient uses a disallowed medication, this use will be recorded as a protocol violation. Protocol violations must be reported to the IRB in accordance with their standard operating procedures.

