10.12 Safety Analyses

The primary safety analysis will summarize ocular treatment-emergent AEs (TEAEs) in the study eye for all treated patients using discrete summaries at the patient- and event-level by system organ class and preferred term for each treatment group. A TEAE will be defined as occurring on or after the day that treatment is initiated. An additional analysis will investigate ocular AEs for the non-study eye. Non-ocular TEAEs will be summarized using discrete summaries at the patient- and event-level by system organ class and preferred term for each treatment group. Treatment-related ocular and non-ocular TEAEs will be summarized similarly. Ocular and non-ocular TEAEs will also be summarized by severity.

The IOP data will be summarized at each visit using both continuous summaries (including change from baseline) and discrete summaries (including the proportion of patients with change in IOP from baseline ≥ 10 mm Hg and the proportion of patients with an IOP ≥ 30 mm Hg that occurs at any time following instillation of study treatment) as well as shift tables.

Slit lamp biomicroscopy and dilated indirect ophthalmoscopic examination measures will be summarized at each visit using discrete summary statistics.

Visual acuity data will be summarized at each visit, using discrete summaries, including change from baseline in the number of lines and the proportion of patients with change from previous visit of ≥ 2 lines.

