9.3 Safety

The Safety population includes all randomized patients who received at least one dose of investigational treatment. The Safety population will be analyzed as treated and will be used for the safety analyses. No data will be excluded for any reason.

10. Patient Disposition

Patient disposition will be presented in terms of the numbers and percentages of patients who were randomized. Patients who are not discontinued from the study will be considered study completers.

The total number of screened subjects with the number and percentage of screen failure subjects and reasons for screen failure will be displayed with the percentages calculated using total number of 13/FEB/2014 Confidential Page 12 of 21

Statistical Analysis Plan Protocol RTA 408-C-1307

Version 1.0

screen failures as the denominator. The number of patients in each of the populations (ITT, PP and Safety) will be displayed by treatment and percentages will be calculated using randomized patients as the denominator.

The number and percentage of patients with major protocol deviations will be summarized by treatment group for all randomized patients. The protocol deviations that will be summarized include: non-compliance with any scheduled study visit, non-compliance with study treatment, use of disallowed concomitant medications, non-compliance with study inclusion or exclusion criteria, non-compliance with study assessment procedures and other. A patient listing will be provided that includes the date of the deviation, the deviation description and the classification of whether the deviation was judged to be major or minor.

The number and percentage of patients prematurely discontinued from study treatment and the reasons for study treatment discontinuation will be summarized by treatment group for all randomized patients. The reasons for study treatment discontinuation that will be summarized include: adverse event (AE), protocol violation, lack of efficacy, administrative reasons, sponsor termination of study, voluntary withdrawal, pregnancy and other. A patient listing will be provided that includes the date of and reason for premature study treatment discontinuation.

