15.5 Intraocular Pressure (IOP)

Intraocular pressure (IOP) will be assessed in both eyes by Goldman applanation tonometry at each visit. Results will be taken from a single measurement and will be recorded in mmHg.

The IOP values and changes from baseline for each eye (study eye and non-study eye) will be summarized using descriptive statistics (number of observations, mean, SD, median, minimum, and maximum values) by visit and eye for each treatment group and for all patients combined. In addition, the proportion of patients with an increase in IOP ≥10 mm Hg from baseline and the proportion of patients with an IOP ≥30 mm Hg at the visit will be presented using frequency counts and percentages. A patient listing of IOP will also be produced.

16. Interim Analyses

There are no planned interim analyses.

17. Changes from Protocol-Stated Analyses

The imputation methodology for the Per Protocol population, described in Section 9.2 of this SAP, differs from that described in the Protocol. The SAP accurately reflects how data will be handled for patients who are discontinued from study treatment due to lack of efficacy.

18. Reporting Conventions

Reporting conventions will adhere when possible to the International Conference on Harmonization (ICH) Guidance E3, "Structure and Content of Clinical Study Reports". All tables and listings will be presented in landscape format. All SAS output for tables and listings will be distributed in PDF files.

19. Revisions History

Documentation of revision to the SAP will commence after approval of the Final version 1.0.

Statistical Analysis Plan Protocol RTA 408-C-1307

Version 307 1.0

20. Tables

Table		Population
Number	Title	Intent-to-Treat
14.1.1	Summary of Analysis Populations, All Patients	Intent-to-Treat
14.2.2.1	Patient Disposition	
14.1.2.2	Patient Disposition	Per Protocol
14.1.3	Significant Protocol Deviations	Safety
14.1.4.1	Demographic Characteristics	Safety
14.1.4.2	Demographic Characteristics	Intent-to-Treat
14.1.4.3	Demographic Characteristics	Per Protocol
14.1.5.1	Non-Ocular Medical History	Intent-to-Treat
14.1.5.2	Ocular Medical History	Intent-to-Treat
14.1.6.1	Non-Ocular Prior and Concomitant Medication Use, Classified by WHO ATC Drug Classification	Intent-to-Treat
14.1.6.2	Ocular Prior and Concomitant Medication Use, Classified by WHO ATC Drug Classification	Intent-to-Treat

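### The SAP tabulates IOP only by visit and drops the protocol's any-time count at 30 mm Hg, so a pressure difference between arms is attenuated once affected eyes are treated

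*Protocol*

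**What the plan says.** **Protocol.** The synopsis asks for the "proportion of patients with an IOP ≥ 30 mm Hg that occurs at any time following initiation of study treatment". Section 10.12 repeats the measure, for a value "that occurs at any time following instillation of study treatment". Both also call for by-visit continuous summaries, the proportion with a change of 10 mm Hg or more, and shift tables.

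**SAP 15.5.** "The IOP values and changes from baseline for each eye (study eye and non-study eye) will be summarized using descriptive statistics" by visit. A rise of 10 mm Hg or more over the baseline value is reported as a proportion, with no any-time wording. For the higher threshold, the SAP states that "the proportion of patients with an IOP ≥30 mm Hg at the visit will be presented using frequency counts and percentages". The any-time count is gone. IOP shift tables are not mentioned, and the table list has a single IOP table. SAP section 17 declares one departure from the protocol, the Per Protocol imputation, and nothing about IOP.

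**Pressure-lowering medication.** Protocol 8.2.1 prohibits "Glaucoma medications or ocular hypertension medications in the study eye". The stated consequence is: "If a patient uses a disallowed medication, this use will be recorded as a protocol violation". Neither Protocol 10.12 nor SAP 15.5 says how later IOP readings from that eye are handled.

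**Which readings reach the tables.** SAP 9.3 states: "The Safety population will be analyzed as treated and will be used for the safety analyses. No data will be excluded for any reason". SAP 6.4 lists unscheduled data but in general leaves them out of summary tables. Protocol 8.4.2 allows IOP to be measured at unscheduled visits.

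**The concern.** Starting pressure-lowering medication is a consequence of the outcome being measured. If one concentration raises IOP, more eyes in that arm are likely to be treated, and their later readings fall. By-visit means and proportions then mix untreated and treated readings, and the mix differs by arm in the direction that makes the arms look alike. A count of patients who ever crossed the threshold avoids this, because later treatment cannot undo a crossing already observed. That is the measure the SAP omits.

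A second gap lies between visits. An eye found high and treated at an unscheduled visit can be back in range by the next scheduled reading, and it may then contribute to no IOP threshold row. Starting the medication is not counted as an IOP event in either document.

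The protocol describes this as the first clinical study of the product, and IOP is one of its five listed safety measures. The IOP table should therefore be able to show a difference if there is one.

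**Working it through.** The documents give no expected IOP rate and attach no test to IOP, so there is no planned figure to reproduce. The check compares the text and then does arithmetic on assumed rates.

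**1. Text comparison**

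| Item | Protocol synopsis and 10.12 | SAP |
|---|---|---|
| IOP of 30 mm Hg or more | any time after treatment starts | at the visit (15.5) |
| Rise of 10 mm Hg or more | no any-time wording | no any-time wording (15.5) |
| Shift tables for IOP | yes | not mentioned (15.5) |
| Readings after pressure-lowering medication | no rule | no rule; no data excluded (9.3) |
| Unscheduled readings | may be taken (8.4.2) | generally not tabulated (6.4) |
| Change declared | not applicable | no (17) |

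**2. Proportion at 30 mm Hg or more**

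Assumptions: new spikes in active eyes are 15% at Day 4 and 5% at Day 8, and in placebo eyes 3% and 2%. Every such eye then starts medication, and a share *s* of treated eyes reads below 30 at later visits.

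- By-visit proportion = new spikes + earlier spikes × (1 − *s*)
- Any-time proportion = sum of new spikes

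Example, *s* = 0.5 at Day 8: active 5 + 15 × 0.5 = 12.5%; placebo 2 + 3 × 0.5 = 3.5%.

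| *s* | Day 4 | Day 8 | Day 15 | Day 21 | Any time |
|---|---|---|---|---|---|
| 0 | 15 vs 3% | 20 vs 5% | 20 vs 5% | 20 vs 5% | 20 vs 5% |
| 0.5 | 15 vs 3% | 12.5 vs 3.5% | 10 vs 2.5% | 10 vs 2.5% | 20 vs 5% |
| 1 | 15 vs 3% | 5 vs 2% | 0 vs 0% | 0 vs 0% | 20 vs 5% |

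If the spikes are instead spread evenly over the four visits (5% vs 1.25% new at each) and *s* = 1, every visit shows 5% vs 1.25%. The any-time count is 4 × 5 = 20% vs 4 × 1.25 = 5%.

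**3. Mean IOP**

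Assumptions: 20% of active and 8% of placebo eyes read 32 mm Hg at Day 4, and all other eyes read 15. Affected eyes are treated, and those that respond read 18 from Day 8.

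- Day 4 difference: (0.20 − 0.08) × (32 − 15) = 2.04 mm Hg
- Day 8, all respond: 0.12 × (18 − 15) = 0.36 mm Hg
- Day 8, half respond and half stay at 32: 0.12 × (0.5 × 17 + 0.5 × 3) = 1.20 mm Hg
- Day 8, none respond: 2.04 mm Hg

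The relative loss when all respond is 1 − 3/17 = 82%. It depends only on the three assumed pressures, not on the event rates.

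**4. Setting post-medication readings aside**

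In the same example, removing those readings at Day 8 leaves only eyes at 15, so the difference is 0.00 mm Hg. That is smaller than the 0.36 obtained from all the data.

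**5. Spikes found between visits**

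Let a share *u* of the 20% and 5% be found and treated at unscheduled visits and be back below 30 at the next scheduled one. An any-time count built from scheduled visits alone gives 20% × (1 − *u*) vs 5% × (1 − *u*). That is 10% vs 2.5% at *u* = 0.5 and 0% vs 0% at *u* = 1. The any-time count must therefore include unscheduled readings.

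**The case against.** A reader might infer that the plan hides an IOP signal altogether. The documents do not support that, for four reasons.

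- The protocol's own measure at 30 mm Hg is cumulative, so later treatment cannot erase a recorded value. The weakness lies in the SAP's replacement.
- A rise first seen at a scheduled visit is tabulated there. In the example for means, the Day 4 table would show 20% vs 8% at 30 mm Hg or more and the full 2.04 mm Hg difference.
- Other outputs give evidence by arm: study-eye medications by drug class (SAP 12.2), major deviations including disallowed medications (SAP 10) and ocular adverse events (SAP 15.1). IOP is also listed by patient.
- No passage says that treated readings count as untreated. Their unflagged entry follows from the rule that no safety data are excluded and the absence of any other rule.

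It would also be wrong to say that a patient who uses the prohibited medication must be kept in follow-up. Protocol 8.6.2 allows discontinuation for protocol violations. Required follow-up is stated for escape medication; others who stop study drug are only encouraged to stay.

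All of this stands and limits the point. The backup is nevertheless partial. The medication table combines prior and concomitant use and is not linked to IOP, the deviation summary does not separate pressure-lowering drugs from other disallowed ones, and the adverse event sections give no IOP value at which an event must be recorded. None of these restores the any-time count.

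**Conclusion.** The point holds as attenuation. Under SAP 15.5, a between-arm IOP difference can shrink at visits after the one where the rise is first seen. A spike found and treated at an unscheduled visit may be absent from the IOP table, though it stays in the listings and appears in the adverse event or medication tables if recorded there. The SAP also drops a protocol-specified measure without declaring it.

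The size cannot be fixed from the documents. Under the assumed early spikes, the Day 15 proportions range from 20% vs 5% (no treated eye responds) to 0% vs 0% (all respond), while the any-time figure stays at 20% vs 5%. These results need some eyes to receive a prohibited medication; if none do, nothing is attenuated. The 82% loss in the mean is a product of the assumed pressures and should not be cited as an estimate.

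IOP is summarised descriptively, with no test or decision rule attached, so no efficacy conclusion is affected. This is an inexpensive improvement to the safety reporting that the sponsor should make.

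**What to change.** In SAP 15.5, and in Protocol 10.12 to match, add by arm the proportion of patients with a study-eye IOP event at any time after the first dose. Define the event as any of:

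- a rise of 10 mm Hg or more from baseline;
- a value of 30 mm Hg or more;
- start of any IOP-lowering medication, taken from the concomitant-medication record.

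Count unscheduled readings, stating this as an exception to SAP 6.4. Show each component separately as well as the composite, so that the protocol's any-time figure at 30 mm Hg can be read directly.

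Keep the by-visit table on all data, and flag post-medication readings in the IOP listing. Do not add a table that sets those readings aside: it removes the affected eyes and can shrink the difference further. If the sponsor means to keep the visit-level wording as the only measure at 30 mm Hg, list that in SAP section 17 as a change from the protocol.

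The cost is SAP and protocol wording, one block of table rows and one listing flag. The medication data are already collected under Protocol 8.2. The reported IOP event rate may look somewhat less favourable. The change concerns analysis only and takes no position on whether or when pressure-lowering treatment is given.
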